Recruitment will be conducted by the Delivery Team (DT). Given that recruitment is to an RCT as opposed to the programme *per se*, the Evaluation Team (ET) will work closely with the DT to ensure that participants are clear about involvement in the study (to reduce the potential for later attrition). Recruitment will be of disadvantaged families with children aged 2-3 years who are eligible for, but not taking up, the 2-year free nursery place offer. Parents/carers will be identified through collaboration with local authorities. The DT Coordinators will work with local authority Heads of Service for Early Years, Early Years Inclusion Officers and Family Centre/ Children's Centre Outreach Teams to recruit families and work with key staff such as Health Visiting Teams, Family Support and other locality team staff to promote and generate referrals to the study.

A minimum threshold for spoken English language fluency will be applied as an inclusion criterion as this would potentially impact on ability to complete the measures used in the trial and to participate fully in the programme (where resources, materials and a suitable home visitor fluent in the primary language used in the home may not be available).

There will be two stages for checking English language thresholds are met. First, participating parents should be able to complete consent forms when help is provided (i.e. by home visitor or family member). Second, at pre-test families will be considered eligible if they are able to complete the forms with data collector assistance. For practical reasons it is not possible to use an external interpreter.

Children experiencing language delay will be included providing that they meet the other eligibility criteria (eligible, but not taking up, the 2-year old offer). Similarly, children will not be excluded due to special needs if it was felt that the family could benefit from inclusion, providing the other criteria were met.

Whilst we are interested in those children with a Child in Need status this will be monitored retrospectively. However, where Local Authorities chose to use referral routes into the programme they will be requested to prioritise this group.

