Sample size calculations were conducted using Stata v15.0. Although the unit of randomisation will be households, in the vast majority of these there will be only one eligible child. Therefore the sample size has been conducted as for an individually randomised trial. Multiple eligible children within a household will be allowed to take part, and in these cases we will use the mean of the scores obtained within the household for statistical analyses. The DT have estimated that they would have capacity to support 160 families in the intervention (40 in each of 4 geographical regions). Using equal randomisation, we aim to recruit 320 families. Assuming scores obtained at baseline and follow up are approximately bivariate normal with a correlation of 0.7 and 20% attrition at follow up (n=64), this sample size (n=256) gives a minimum detectable effect size (MDES) of 0.25 in a two-sided test of the difference between groups adjusted for baseline with nominal type 1 and 2 error rates of 5% (i.e. alpha of 0.05) and 20% (i.e. power of 80%), respectively. This would mean that this study would be able to detect lower effect sizes than those in the US studies discussed above.

Outcome measures

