The primary child outcome will be the **British Picture Vocabulary Scale** (BPVS-III; Dunn, Dunn and NfER, 2009) administered one-to-one by independent assessors blind to condition, trained and organised by the University of York. The BPVS-III is a standardised measure of receptive vocabulary based upon the Peabody Picture Vocabulary Test (PPVT: Dunn and Dunn, 1981) which has been used in a number of US evaluations of ParentChild+. The basic testing activity involves showing the child a series of images, four to a page, one of which will match a pre-specified word the assessors says to the child. The child is required to point to the picture they believe most closely resembles the word given. It takes between 5 and 8 minutes to administer. As no reading or verbal response is required it is considered suitable for young children and those for whom English is an Additional Language. It is also easy to administer and takes a relatively short time to complete enabling children to remain focused during the assessment period. The BPVT-III has proven to be highly correlated with later literacy acquisition (Dunn, Dunn and NfER, 2009). It is standardised for children aged 3 to 16 years, but can also be administered to two year olds. The previous version of the BPVS (BPVS-II) was standardised for two and a half year old children. Consequently we expect it to be suitable to be administered to two-year-olds but we will pilot the BPVS-III prior to its use to confirm its suitability for this study. The pilot will take place with 10-15 children aged between 18 months and three years of age recruited from nurseries and local parent- and play-groups in order to confirm that there is no floor effect. We will aim to have a mixture of children for whom English is an Additional Language and who are eligible for the two-year old free nursery places. The measure will be regarded as suitable providing there is variation in response and no floor effects are detected. Assuming its suitability, the BPVS-III will form the primary pre-test and be administered by data collectors from the University of York prior to randomisation.

The secondary outcomes are:

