analysed according to the group they were assigned to (either intervention or control) regardless of adherence to that condition or not (i.e. participants allocated to receive the intervention will be analysed within the intervention group even if they do not participate in the programme). Where participants withdraw from the programme this shall not be classed as withdrawal from the study and participants will be asked to continue participating in the data collection and data processing aspects of the study. Baseline data will be summarised descriptively, both as randomised and as included in the primary analysis, with no formal comparisons being undertaken. Both adjusted and unadjusted summaries of the outcome measures will be presented, with p-values and appropriate 95% confidence intervals (CI) given for all between group comparisons.

A CONSORT diagram will be produced to show the flow of households and participants through the trial.

Primary Analysis

Linear regression will be used to compare raw BPVS-III scores between the two groups. Group allocation, baseline (raw) BPVS-III score, age and Local Authority will be included as fixed effects in the model. Participants with either age missing or baseline BPVS-III score missing will have these imputed with the relevant strata specific mean. Hence all participants with non-missing BPVS-III scores at follow up will be included, as randomised, in the primary analysis model. The BPVS-III is a norm-referenced test and standardised for children aged 3 years to 16 years and 11 months. However the children being recruited as part of this trial will all be less than three years old at baseline, meaning no age standardised scores exist. Hence the inclusion of age as a covariate. The inclusion of age as a covariate is also likely to increase the precision of the estimate of the treatment effect. Inferences regarding the effectiveness of the ParentChild+ programme will be based on the adjusted difference in mean score between the two groups suggested by this model. Effect size will be summarised using Hedges' g and associated 95% CI.

Further analyses of primary outcome

Further analyses of the primary outcome will be conducted to investigate the possible influence of non-compliance on the result of the primary analysis, and to assess the sensitivity of the primary analysis to variation in the missing data assumptions.

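### The primary model gives a child with no baseline BPVS-III score the Local Authority mean and has no term marking the imputation; an indicator would protect precision at almost no cost, and the handling of unscorable children needs stating

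*Protocol*

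**What the plan says.** **Imputation and model.** Under Analysis plan, Primary Analysis, the protocol states: "Participants with either age missing or baseline BPVS-III score missing will have these imputed with the relevant strata specific mean". Randomisation is stratified by Local Authority only, so the imputed value is a Local Authority mean. The same paragraph lists the linear regression terms: allocation, raw baseline BPVS-III, age and Local Authority. No term distinguishes an observed baseline from an imputed one.

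**Who is tested.** All children are under three at baseline. Of the test, the Outcome measures section says: "It is standardised for children aged 3 to 16 years, but can also be administered to two year olds". It makes use of the test conditional on a pilot in 10–15 children showing variation in response and no floor effect. The Participants section adds: "Children experiencing language delay will be included providing that they meet the other eligibility criteria", and special needs are not in themselves an exclusion.

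**When baseline is collected.** The Randomisation section allocates households only after baseline testing is complete. The Participants section counts a family as recruited only once the pre-test measures are done.

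**Planned precision.** Sample size calculations: "Assuming scores obtained at baseline and follow up are approximately bivariate normal with a correlation of 0.7" and 20% attrition, "this sample size (n=256) gives a minimum detectable effect size (MDES) of 0.25".

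**The concern.** The planned MDES relies on the baseline score explaining about half of the outcome variance (0.7² = 0.49). A two-year-old who cannot be scored on a test standardised from age three is plausibly among the weakest. If that child's baseline is recorded as missing, the stated rule enters the child as average for the Local Authority. The child's low follow-up score then goes into the residual variance, and the standard error of the treatment effect rises.

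Nothing else in the protocol picks this up. The further missing-data analyses deal with missing outcomes. The trigger for multiple imputation counts cases excluded from the primary analysis, and a child with an imputed baseline is not excluded.

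What is at stake is precision only. It would be hard to recover by recruiting more families, because delivery capacity limits the intervention arm to 160.

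**Working it through.** **Inputs from the protocol.** Two-sided alpha 0.05, power 80%, correlation r = 0.7, 256 families analysed (128 per arm), four strata, 1:1 allocation.

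**Assumed, because the protocol does not give them.** The share m of missing baselines, the mechanism of missingness and, in the simulation, an age–baseline correlation of 0.4.

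**Step 1: the protocol's own figure.** In outcome SD units, MDES = (1.960 + 0.842) × √(2/128) × residual SD = 0.3502 × residual SD. With full baselines the residual variance is 1 − 0.49 = 0.51, so MDES = 0.3502 × 0.714 = 0.250. Also 256/0.8 = 320. The stated figure reproduces.

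**Step 2: missing at random, stated rule.** The residual variance is 1 − (1 − m) × 0.49.
- m = 5%: 0.5345, MDES 0.256.
- m = 10%: 0.559, MDES 0.262.

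An indicator changes nothing here, because the missing children are average.

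**Step 3: worst case, exactly the lowest scorers missing, stated rule.** The residual variance is 1 − 0.49 × (1 − m) × V₁, where V₁ is the variance of a standard normal truncated below its m-quantile.
- m = 5%: V₁ = 0.810, variance 0.623, MDES 0.276–0.277.
- m = 10%: V₁ = 0.712, variance 0.686, MDES 0.290.

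**Step 4: worst case with an indicator.** Only the spread within the missing group is left unexplained. The residual variance is 0.51 + 0.49 × m × V₀, where V₀ is the variance below the quantile.
- m = 5%: V₀ = 0.138, variance 0.513, MDES 0.251.
- m = 10%: V₀ = 0.169, variance 0.518, MDES 0.252.

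In this case, power for an effect of 0.25 is 71.7% (m = 5%) and 67.6% (m = 10%) under the stated rule, against 79.7% and 79.3% with the indicator.

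**Step 5: the protocol's model with age included, by simulation.** Trials of n = 256 were simulated with four strata, taking MDES as the same multiplier times the mean standard error. In the intermediate mechanism low scorers are more likely to be missing (logit slope −1.5 per SD). Simulated values run slightly above the formula because extra terms are estimated.

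| Missing | Mechanism | Stated rule | With indicator |
|---|---|---|---|
| 5% (about 13 of 256) | random | 0.257 | 0.257 |
| 5% | intermediate | 0.264 | 0.255 |
| 5% | lowest scorers | 0.277 | 0.253 |
| 10% (about 26 of 256) | random | 0.263 | 0.263 |
| 10% | intermediate | 0.274 | 0.260 |
| 10% | lowest scorers | 0.289 | 0.254 |

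At 1–2% missing (about 3 to 5 children) the stated rule gives 0.252–0.265 across the mechanisms. Having age in the model recovers little of the loss.

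**Step 6: validity.** In 6,000 simulated trials per scenario without the age term, with the lowest scorers missing at up to 20%, the stated rule gave mean estimates of 0.247–0.251 for a true effect of 0.25. Its type I error was 4.7–5.3%.

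**The case against.** The strongest objection is that missing baselines should hardly occur. Randomisation follows completed baseline testing, and a family is not recruited until the pre-test is done. The imputation sentence is a fallback and states no expected rate. The pilot is a further check on suitability. An unscorable child might be given a low raw score, or be treated as not having completed the pre-test, and then the rule would never apply to that child. This stands to a large extent: it is why the size of the loss cannot be read from the protocol and why the 1–2% figures matter. It does not settle the question, because the protocol provides for missing baselines and does not say which of these treatments applies.

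It can also be said that the SAP may add an indicator. That is possible, but it would change the list of model terms written in the protocol.

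A reader might infer that entering weak children as average biases the treatment effect. It does not. The score precedes randomisation and the imputation depends on stratum, not arm; the simulations show neither bias nor an inflated type I error.

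A reader might also carry the argument over to the ASQ-3 and HLE Index models, which use the same imputation rule. Those measures are completed by the parent, with help from the data collector if needed, so a child's inability to be tested does not make them missing.

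**Conclusion.** The point holds as an inexpensive improvement to a stated rule; the analysis as written is valid. If unscored children are treated as missing and are mainly low scorers, the stated model loses precision that one covariate would largely restore. At 10% missing the MDES is 0.274 (intermediate) to 0.289 (worst case) under the stated rule, against 0.260 and 0.254 with the indicator. At 1–2% missing the loss is small, and under random missingness the indicator gains nothing.

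The documents do not support saying that the 0.25 MDES has in fact been eroded or that the trial is underpowered. Both the missing share and the mechanism are assumptions here. The protocol does leave a gap to close: its requirement for a completed pre-test and its provision for missing baselines are not reconciled for a child who was tested but could not be scored.

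**What to change.** 1. Keep the stratum-mean imputation, computed without regard to allocation, and pre-specify in the primary model a 0/1 indicator for missing baseline BPVS-III. It drops out if no baseline is missing.
2. State whether a child who was tested but could not be scored counts as having completed the pre-test, and whether the score is recorded as missing or as a low raw score, so that the Randomisation, Participants and Primary Analysis sections agree.
3. An indicator in the ASQ-3 and HLE Index models is optional, since the unscorable-child argument does not reach them.

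The cost is a sentence or two in the protocol or SAP, fixed before outcome data are seen, and one degree of freedom. No new data are needed.

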- **Ages & Stages Questionnaire[®], Third edition (ASQ[®]-3)** (Squires & Bricker, 2009). This 30-item parent/carer-completed measure is standardised for children aged one month to 5½ years, so is suitable for this age group (with different questionnaires depending on child developmental stage). It measures communication, gross motor skills, fine motor skills, problem solving, and personal-social skills. This measure will also be completed at pre-test. The ASQ-3 will be used to identify whether or not the programme increased verbal and non-verbal interaction, developed positive behaviours and

encouraged early literacy skills. In addition, fine motor skills are supported by the programme and have been associated with school readiness and reading outcomes in the early stages of schooling (Cameron et al., 2012). They are also associated with early handwriting (as measured by the literacy sub-scale of the EYFS) and considered a part of a rich Home Learning Environment (e.g. through the encouragement of drawing and painting) (Melhuish, 2010). Consequently only three of the five subscales will be administered: communication, personal-social, and fine motor to reduce participant burden (18 items, 6 in each subscale).

- The Home Learning Environment will be assessed using the **Home Learning Environment (HLE) Index** (Melhuish, 2010). This 16-item self-reported measure includes items which relate to activities undertaken with the child and their frequency. Items correspond to concrete parenting behaviours based on evidenced relationships to children's development. This scale has been previously used in the National Evaluation of Sure Start and the Millennium Cohort Study.

Both these measures will be administered at pre-test as well as post-test.

To aid completion of parent-report measures, these will be delivered to families by data collectors who will provide time for independent completion during their visit. They will be trained to assist parents/carers to complete the measures if needed. Given the nature of the sample we recognise that much of the data is self-complete although we do have an independently-administered primary outcome. We feel that this will still provide valuable results (cf. Bennett, S., 2017).

The recruitment and data collection flow chart can be found in the Appendix.

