We also intend to follow children into the school system with permission to access NPD data at a later stage. To do this, we would need to obtain signed parental consent so that the Local Authorities can share information on school destination using existing information from the project, including child name, date of birth and home postcode. We plan to include in the Memorandum of Understanding and the Data Sharing Agreement with Local Authorities agreement to provide details on child's school destination in February 2021 and February 2022. These two data collection points reflect the expectation that the recruited cohort will enter school in either September 2021 or September 2022 (depending on age at, and month of, recruitment). Allocation of school places is generally conducted prior to February in the preceding academic year. Analysis of NPD data will be conducted as part of a longer term follow up done in addition to the present evaluation. It is anticipated that the focus will be on the Reception Baseline Assessment, which measures communication, language, literacy skills and maths, to assess school readiness and emergent literacy skills. A longer term follow-up is also anticipated. Given that the KS1 assessments will become optional in 2023 (the year our older cohort of children will enter Year 2) and that the phonics assessment administered in Year 1 only measures one discreet aspect of the skills needed in learning to read we anticipate this being the Early Years Foundation Stage profile, focusing on communication and language, personal, social and emotional development, and literacy attainment.

Analysis plan

The statistical analysis will follow the most recent EEF guidance, and will be described in detail in a Statistical Analysis Plan (SAP) prepared within three months of the last participant being randomised. All analyses will be conducted following intention-to-treat (ITT) principles, using two-sided statistical tests at the 5% significance level. This means that participants will be

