A Complier Average Causal Effect (CACE) analysis will be conducted to obtain an estimate of the average causal effect of receiving the programme as planned, while accounting for measured and unmeasured confounding between treatment adherence and outcome. For the purposes of this trial, compliance will be defined dichotomously as delivery of 78 of the 92 programme sessions (85%) with each session being approximately 30 minutes long. This is based on compliance as defined by, and used for routine data analysis by the original developers in the US. An additional compliance analysis based on continuous data (ie. number of overall sessions completed) will also be conducted.

The possible impact of missing data on the conclusions drawn from the primary analysis will be explored with a range of different methods. Available reasons for withdrawal/missingness will be examined to inform whether these are plausibly related to outcome or not. Baseline variables associated with missing primary outcome data will be identified using logistic regression, and the primary analysis model will be refitted including these as additional covariates in order to make the missing at random (MAR) assumption more plausible. If greater than or equal to 5% of cases are excluded from the primary analysis due to missing data, then the MAR assumption, and possible influence of data observed post randomisation

(e.g. compliance data) will be explored using multiple imputation. Finally the sensitivity of results to the outcome data being missing not at random (MNAR) will be explored using a pattern mixture modelling approach.

Secondary Analyses

Data will be collected for three subscales of the ASQ-3 with the responses in each scale being used to generate a score between 0 and 60. These will be analysed individually using three linear regression models adjusting for allocation, baseline score and local authority. Any missing baseline scores will be imputed with the strata specific mean prior to analysis. Hence all participants with non-missing scores at follow up will be included in the models.

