The responses to the 16 items of the Home Learning Environment Index will be combined to give an overall score, with higher scores being indicative of a more positive home learning environment. This score will be analysed using a linear regression model adjusting for allocation, baseline score and local authority. Any missing baseline scores will be imputed with the strata specific mean prior to analysis. Hence all participants with a non-missing Home Learning Environment Index score at follow up will be included in the model.

Subgroup Analyses

Three pre-specified exploratory analyses of the primary outcome will be conducted to investigate the possibility of treatment effect heterogeneity among trial participants. Variation in treatment effect will be explored across different levels of the following three baseline characteristics; Children in Need status, (a binary classification of whether or not the child has ever been a “Child in Need” at any time in their life up until baseline), English as an Additional Language (again a binary classification) and baseline score on the ASQ communication subscale. Baseline score for the ASQ will be used for this subgroup analysis because, unlike the BPVS-III, it is age standardised for children as young as 1 month, and therefore appropriate for the developmental stage of participating children at baseline. The communication subscale will be used as it aligns more closely with the construct measured by the BPVS-III than either of the other two ASQ scales that are being collected.

In all three cases treatment effect heterogeneity will be investigated by examining whether or not the inclusion of the main effect (if not already present), and its interaction with randomised group, in the model used for the primary analysis leads to a significant improvement in model fit. If the inclusion of such interactions does lead to improved model fit, then this model will be used to assess between group differences within strata and provide associated inference.

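### Adding age to the HLE Index model, and for consistency to the three ASQ-3 models, would be a free but modest gain in precision; leaving it out is not an error of validity.

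*Protocol*

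**What the plan says.** **Secondary models.** In the Protocol's Analysis plan, under Secondary Analyses, each ASQ-3 subscale is scored from 0 to 60 and the three are analysed with "three linear regression models adjusting for allocation, baseline score and local authority". For the HLE Index: "This score will be analysed using a linear regression model adjusting for allocation, baseline score and local authority". Both lists are complete as written. Neither includes age, and no reason is given.

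**Primary model.** Under Primary Analysis: "Group allocation, baseline (raw) BPVS-III score, age and Local Authority will be included as fixed effects in the model". Two reasons are given for age. The first is that the children are too young for BPVS-III norms, "meaning no age standardised scores exist. Hence the inclusion of age as a covariate". The second is added to it: "The inclusion of age as a covariate is also likely to increase the precision of the estimate of the treatment effect".

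**How the instruments handle age.** Outcome measures describes the ASQ-3 as standardised across early childhood, "with different questionnaires depending on child developmental stage". Subgroup Analyses says of the ASQ that, "unlike the BPVS-III, it is age standardised for children as young as 1 month". The HLE Index is described as a 16-item self-report of activities with the child and how often they happen. Nothing is said about age standardisation.

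**Availability of age.** Age is needed for the primary model, which also has a rule for imputing it when missing. The information held for later school linkage is listed as "including child name, date of birth and home postcode".

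**The concern.** The protocol accepts that age can sharpen the treatment comparison in the primary model, then fixes four secondary models without it and does not say why. Children enter as two-year-olds through rolling recruitment, and randomisation is stratified by Local Authority only, so age varies and is balanced only by chance.

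If age still predicts the follow-up score once baseline is in the model, two things are lost. The confidence intervals are somewhat wider than they need be, and a chance age difference between arms stays in the secondary estimates. For the HLE Index, the frequency of activities with a child could change with the child's age. For the ASQ-3, any such effect would have to be age variation left within or between the stage-specific forms.

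**Working it through.** **1. Inputs.** From the Protocol, Sample size calculations: 320 families, 20% attrition, 256 analysed (128 per arm), baseline to follow-up correlation 0.7, two-sided alpha 0.05, power 80%, MDES 0.25. The correlation of 0.7 is stated for the sample size calculation only; carrying it over to the ASQ-3 and HLE Index is an assumption. The partial correlation r of age with the follow-up score, given the baseline score, is not in the documents and is assumed over a range.

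**2. The plan's own figure.** MDES = (1.960 + 0.842) × √(1 − 0.7²) × √(2/128) = 2.802 × 0.714 × 0.125 = 0.250. The stated 0.25 is reproduced, and power at 0.25 is 79.97%.

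**3. Effect of adding age.** The residual variance is multiplied by (1 − r²), and the standard error and MDES by √(1 − r²).

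| Assumed r | Residual variance falls by | Standard error falls by | MDES, baseline correlation 0.7 | MDES, baseline correlation 0.5 (assumed) |
|---|---|---|---|---|
| 0 (age not prognostic) | 0% | 0% | 0.250 | 0.303 |
| 0.1 | 1% | 0.5% | 0.249 | 0.302 |
| 0.2 | 4% | 2.0% | 0.245 | 0.297 |
| 0.3 | 9% | 4.6% | 0.239 | 0.289 |

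**4. Cost.** The current models have six parameters: intercept, allocation, baseline score and three for the four Local Authorities. Residual degrees of freedom are 256 − 6 = 250, and 249 with age added.

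**5. Validity check.** 4,000 trials were simulated with no treatment effect, 256 children, baseline correlation 0.7, r = 0.3 and an assumed correlation of 0.4 between age and baseline score. Local Authority was left out for simplicity.

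| | Without age | With age |
|---|---|---|
| Mean estimated effect | −0.001 | −0.001 |
| Mean standard error | 0.0893 | 0.0853 |
| Rejection rate at 5% | 5.1% | 4.8% |

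There is no bias. Both rejection rates agree with 5% within simulation error (√(0.05 × 0.95/4,000) = 0.3 percentage points). The ratio of standard errors, 0.0853/0.0893 = 0.955, agrees with √(1 − 0.3²) = 0.954.

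**6. Chance imbalance in one trial.** If age, given baseline, differs between arms by z of its own standard errors, the estimate without age shifts by about r × z standard errors of the treatment effect. At r = 0.3 and z = 2 that is 0.6 × 0.0893 ≈ 0.05 SD. An imbalance that large is unusual, and such shifts average to zero over randomisations.

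**The case against.** The best defence is that the difference between the models is deliberate. The first reason for age in the primary model is that raw BPVS-III scores must be used because the children are below the normed range; precision is a further benefit. The Subgroup Analyses section contrasts the ASQ with the BPVS-III on exactly this point, so the first reason does not carry over to the ASQ-3. Models for different outcomes need not share covariates, and adjusting for the baseline score and the stratification factor is a coherent prespecified choice. The gain rests on an assumed correlation and may be close to nil. The SAP was not available here and may settle the matter.

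Most of this stands. Three stronger readings are tempting, and the documents support none of them:

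- **That the secondary estimates are biased or their tests invalid.** Randomisation rules this out in a linear model, and the simulation agrees.
- **That stage-specific forms make ASQ-3 scores incomparable across ages.** Such forms are how the instrument takes account of age. The text also says that the form depends on developmental stage; that age itself decides it is an inference, though a reasonable one.
- **That the protocol contradicts itself by dropping its precision argument.** Precision was the additional reason, not the only one, and no stated figure changes.

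The defence does not reach the HLE Index. It is not described as age standardised, so both reasons given for age in the primary model could apply to it. Whether its scores do move with age once the family's baseline score is in the model is not shown either way. For the ASQ-3, the documents do not show that the forms remove all age variation from the 0 to 60 score.

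**Conclusion.** Minor. The four secondary models leave out a baseline covariate that is already collected and already in the primary model. Adding it is a free improvement; leaving it out is not a mistake. The case is strongest for the HLE Index and weaker for the ASQ-3, where only residual age variation within or between forms could matter.

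For an assumed partial correlation of 0.1 to 0.3, the standard error falls by 0.5% to 4.6%. On the primary outcome's planning assumptions the MDES moves from 0.250 to between 0.249 and 0.239. If age is unrelated to the outcome given baseline, nothing is gained and almost nothing is lost. The range of r is assumed, as is the use of the 0.7 baseline correlation for these outcomes.

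**What to change.** In the Protocol's Secondary Analyses section, or in the SAP before outcome data are seen, add age at baseline as a fixed effect to the HLE Index model and, for consistency, to the three ASQ-3 models. Apply the primary model's rule for missing age, which is the stratum-specific mean. The primary model text says only age, so state the time point once for all models. If the authors prefer to leave age out, one sentence giving the reason would be enough, in particular for the HLE Index.

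The cost is one phrase and one degree of freedom of about 250. No new data are needed, and the sample size and the primary analysis do not change.
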